4.1 INTRODUCTION

Recent data suggest that initiation of antiretroviral therapy very early after HIV acquisition can confer several benefits. These include reduction in the size of the HIV reservoir and decrease in HIV-associated systemic inflammation that has been linked to non-AIDS mortality in HIV-infected participants, even when HIV replication is effectively controlled by antiretroviral therapy (ART). In addition, some patients who are treated very early appear to effectively control HIV replication years later when ART is discontinued, sometimes referred to as a functional cure. However, very early initiation of ART (in Fiebig stages I or II [F1 or FII] prior to seroconversion) does not prevent the establishment of HIV reservoirs, which eventually expand in most patients when ART is discontinued [1, 2]. Early ART initiation is, nonetheless, associated with preservation of CD4+ T cells, preserving normal gut microbiota, averting a major driver of HIV-related immune activation, and limiting the size of the HIV reservoir [3]. When, by contrast, ART is initiated after seroconversion (in Fiebig stage III [FIII] or later), many HIV-associated changes have already occurred, including seeding of HIV reservoirs, damage to GI mucosa, and initiation of inflammatory cascades [3]. Some if not all of these effects may be related to the development of dysbiosis (a markedly different composition of the gut microbiota that might itself drive continued inflammation).

Since ART initiation within weeks of HIV acquisition is not a viable public health strategy, it is important to more completely understand the *relative long-term benefits* of initiating ART at very early times after infection (F1-II) as opposed to after a short (during FIII-V) or longer delay (at 24 weeks). Because most HIV-infected individuals come to medical attention long after they have been infected, data on individuals with known infection dates, especially those who were infected very recently, is a valuable resource. The MERLIN study of HIV-infected (HIV+) participants will allow the collection and analysis of clinical data and biologic specimens at multiple time points from HIV+ participants with known infection dates in Lima. It will focus on studies of HIV clinical course which incorporate data on time of infection, duration of infection prior to initiation of antiretroviral therapy (ART), and molecular markers of infection such as inflammation and immune dysfunction (including innate immune responses), size and location of HIV reservoirs, and changes in the microbiome. In addition, it will follow participants clinically, with collection of data such as CD4 count, neurocognitive function etc. The effects of alcohol on microbial translocation and pro-inflammatory cytokines are not unlike early changes after HIV infection [4-6]; however, alcohol's role in HIV pathogenesis and progression is not well defined. Since the possibility that high-level alcohol use can mitigate the benefits of early ART is emerging as a potentially important public health issue, the MERLIN study will evaluate the impact of alcohol use as well as time of ART initiation on HIV pathogenesis in Peruvian MSM and TGW in whom high-level alcohol use is common.

The overarching hypotheses of the MERLIN study are as follows: 1. Initiation of ART soon after HIV infection will dampen perturbations of GI microbiota, reduce HIV-induced inflammatory

changes, and decrease seeding of the reservoir. Initiation of ART in FI-II will have the greatest benefit. CD4 counts and peripheral inflammatory markers in the FIII-V group and the group treated at 24 weeks will approach those in the FI-II group at 1.5 and 3.5 years after ART initiation; in contrast, changes in the GI microbiome and the HIV reservoir over time will be more modest. 2. Irrespective of the time of ART initiation, alcohol use will compound the negative effects of HIV to generate greater levels of dysbiosis, microbial translocation, up-regulation of inflammatory pathways, and seeding of the HIV reservoir.

Specimens from the *SABES* and *MERLIN* studies will be used for a series of laboratory investigations probing the mechanisms by which early treatment reduces the HIV reservoir and HIV-associated inflammation, and seeking to determine how soon after HIV acquisition ART must be initiated to confer these beneficial effects. The most in-depth studies will prioritize participants enrolled during the latter half of the *SABES* study who had large PMBC collections at the time of HIV diagnosis and throughout follow-up. These include the following 3 groups based on time of ART initiation: a) *Immediate*: during FI-II (N~20), b) *Early*: during FIII-V (N~35) or c) *Deferred*: at 24 weeks after diagnosis (N~55). A small number of additional studies may be conducted on all participants in the *SABES* study: a) *Immediate*: during FI-II (N~35), b) *Early*: during FIII-V (N~72) or c) *Deferred*: at 24 weeks after diagnosis (N~115). The *MERLIN* study will assess outcomes after 1.5 and 3.5 years after initiation of ART in these MSM and TGW. The results will be evaluated every 6 months during the follow-up of the participants in the study (up to the end of 2022). Laboratory analyses will be conducted in Lima, Perú and Seattle, WA as well as in the laboratories of our collaborators at University of California, San Francisco (UCSF) and University of Montreal (UoM). Additional neuropsychiatric and biologic data will be collected to evaluate neuroinflammation and cognitive changes in early HIV infection (collaborators at UCSF, Yale, and UNC).

4.2 JUSTIFICATION

Early ART initiation is associated with preservation of CD4+ T cells, reduced immune activation (lower levels of CD4+ and CD8+ T cell activation and lower soluble inflammatory markers), lower total HIV DNA levels, and lower cell-associated RNA levels [7]. Recent studies suggest that very early initiation of ART (prior to seroconversion in humans or before detection of viremia in non-human primates) does not prevent the establishment of HIV reservoirs, which eventually expand when ART is discontinued [2, 8]. However, early initiation of ART prevents loss of gut Th17 cells thereby reducing HIV-related immune activation and limits the size of the HIV reservoir [1, 3]. Drug and/or alcohol use in North and South American MSM is associated with increased risk of acquiring and transmitting HIV, and we hypothesize it will influence the course of HIV infection as well. In Peru, where we have enrolled a cohort of MSM/TGW with acute or recent HIV infection, alcohol use is common. In a recent study, 52% of Peruvian MSM reported alcohol use during sex while only 5% reported concomitant drug use. MSM from the US participating in the same study reported drug and alcohol use of 39% and 38%, respectively [9]. A 2011 survey of 5,148 gay and bisexual men in 5 Peruvian cities reported alcohol use disorder (AUD), defined as a score ≥ 8 on the Alcohol Use Disorder Identification Test (AUDIT), in 63% of respondents [10, 11], five times higher than that reported by males in the general Peruvian population [12].

4.2.1 Timing of ART Initiation and Progression of HIV Disease

Even in the setting of suppressive ART, persistent elevations in T cell activation and systemic inflammation appear to play a central role in HIV disease progression. Early ART initiation is associated with lower levels of CD4⁺ and CD8⁺ T cell activation, lower total HIV DNA levels, and lower cell-associated RNA levels in subjects with virologic suppression [7]. In a small number of individuals who were treated very early and then stopped ART, viral suppression continues off therapy [13-15]. Six months of ART initiated shortly after seroconversion (during FIII) improved many immune parameters, although not to the level seen when ART is initiated prior to seroconversion (during FI-II) which resulted in near normal (HIV-uninfected) levels for some parameters [3]. These results raise the question of how to translate these findings to a clinical setting. Recent studies suggest that initiation of ART during hyper-acute infection (i.e., Fiebig stages I and II) may be optimal, but detecting such individuals and linking them rapidly to care pose substantial logistical challenges.

4.2.2 Microbial Translocation, GI Microbiome, and Inflammation in HIV Disease

The GI mucosa is involved in HIV-induced inflammation directly through microbial translocation, which results in increased levels of circulating LPS [16], and indirectly through up-regulation of inflammatory responses in dendritic cells in response to IFN- γ and HIV Tat and Nef. This in turn has detrimental effects on Th17 cells in the gut mucosa [17, 18], leading to impairment of mucosal integrity. Alterations in the gastrointestinal (GI) microbiome, called dysbiosis, also contribute to these inflammatory processes [19, 20]. Dysbiotic bacteria enriched in HIV infection produce tryptophan catabolites (e.g., of the kynurenine pathway) which are linked to inflammation and have been associated with translocation of microbial products into the systemic circulation [21, 22]. Thus, the bacterial communities in HIV-infected individuals may be important drivers of the inflammatory processes that contribute to disease. Importantly, effective ART does not completely reverse the immunopathologic changes in GI mucosa in all subjects, raising the possibility that differences among ART-treated subjects may be related to whether ART was initiated prior to 'irreversible' establishment of dysbiotic GI microbial communities.

4.2.3 Alcohol Effects on Microbial Translocation and the GI Microbiome

Importantly for this protocol, alcohol use has also been linked to microbial translocation and increased levels of endotoxins, such as lipopolysaccharide (LPS), in the portal and systemic circulation. Binge drinking in healthy individuals with no history of AUD results in significant, rapid, and transient increases in serum LPS and 16S rDNA, as well as lipoprotein binding protein(LBP) and soluble CD14 (sCD14) [23], likely due to microbial translocation from the gut to the circulation. Gut microbiome shifts in AUD include reductions in the normally dominant species and enrichment of Gammaproteobacteria and depletion of Bacteroidetes [4], two taxa that are similarly altered in the gut of HIV-infected subjects and linked with HIV disease progression [19, 21, 22]. Thus, alcohol use may exacerbate microbial translocation, inflammation and HIV disease progression by inducing qualitative and/or quantitative changes in these microbial communities.

4.2.4 Alcohol Use, Systemic Inflammation, and Immunity

Innate immune responses appear to initiate the inflammatory cascade linked to alcohol use in animals and in humans [24]. Chronic alcohol consumption has been linked to increases in

circulating levels of LPS, the pro-inflammatory cytokines [5], and acute-phase proteins [6]. These changes are likely mediated at least in part by microbial translocation: thus, microbial pathogen-associated molecular patterns interact with host receptors and trigger downstream transcription and expression of inflammatory genes. Alcohol may also interfere with granulocyte and monocyte production [25], impair the function of dendritic and phagocytic cells [26] and decrease natural killer (NK) cell activity [27].

4.2.5 Effect of Alcohol on HIV Progression is Unclear

There is substantial overlap between the effects of alcohol and HIV on microbial translocation, changes in GI flora, and systemic inflammation. Indeed, some *in vitro* and animal studies link alcohol use to higher plasma HIV/SIV RNA viral loads (VL) [28] and accelerated progression of SIV disease [29], although this finding has not been replicated in all studies [30]. Human studies of alcohol and HIV infection report mixed results; some small studies suggest poorer outcomes [31, 32] while larger cohort studies found no effect on VL or CD4⁺ T cell counts in ART-naïve or treated patients [33]. The differences may be due to unmeasured confounders, poor ART adherence among treated patients, and/or inaccurate assessment of alcohol use (e.g., due to single or widely-spaced measurements, social desirability bias, and use of non-standard definitions). Regardless, the aforementioned detrimental effects of alcohol on microbiome composition, microbial translocation, and systemic inflammation suggest that it may exacerbate HIV disease, and that treatment of AUD in the context of HIV infection may help to resolve inflammation and diminish the viral reservoir.

4.2.6 HIV Integration Sites

Recent studies of individuals who initiated ART during chronic infection [34, 35] indicate that HIV integration into genes associated with cancer or cell cycle regulation confers a survival advantage to specific cells, apparently the result of increased proliferation and formation of clonal populations that persist during suppressive ART. Identifying which early integration events lead to proliferation and persistence of infected cells may suggest novel interventions to reduce or clear the HIV reservoir that is limited in size due to early ART. We expect that participants who initiate ART early vs. later after primary infection will have fewer unique integration sites prior to initiation of ART and at 18 and 42 months will have fewer proviruses in genes associated with cancer and cell proliferation. Also, we expect that AUD will correlate with T cell activation and inflammatory markers. Therefore, we hypothesize that individuals with low alcohol use will have relatively fewer unique integration sites at all time-points compared to those with high use who initiate ART at the same Fiebig stage, and at 18 and 42 months will have fewer proviruses in genes associated with cancer and cell proliferation.

4.2.7 Neurocognitive Impairment

HIV-associated neurocognitive disorders (HAND) are caused by the impact of HIV infection on the central nervous system (CNS). HIV infection of the CNS is associated with neuronal damage, inflammation and, in approximately 40% of treated individuals, cognitive impairment [36-38]. Both CNS pathology and cognitive impairment can persist despite antiretroviral therapy (ART) when it is initiated during established HIV infection; and cognitive impairment may associate with persistent HIV replication and HIV-driven inflammation in the CNS. One intriguing possibility is that CNS HIV persistence may be reduced by very early initiation of ART. In collaborative studies

of individuals treated immediately with acute HIV infection in Thailand [41, 42], we have shown that key markers of inflammation in the CNS quickly normalize and that cognitive function remains normal over the first 6 months of longitudinal follow-up[43]. Among HIV-infected individuals in the US, we found that those initiating ART earlier in the first year of HIV infection (i.e., during “recent” HIV infection) had significantly better cognitive function after a year of ART than did those in whom treatment was more delayed. These observational data strongly suggest—but do not prove—that there is some window in the first year of infection (i.e., during acute and/or recent infection) during which ART can keep HIV from developing the ability to replicate efficiently and persist locally in the CNS on ART. Both alcohol and stimulant use can augment systemic inflammation, increase local neuroinflammation and cause direct neuronal injury. Alcohol-induced neurotoxicity overlaps with HIV mechanisms of neuropathogenesis through oxidative stress, overproduction of pro-inflammatory factors, impairment of blood–brain barrier and glutamate associated neurotoxicity [44]. Thus, it is possible that higher psychostimulant and alcohol use can lead to accelerated or less reversible neurologic and neurocognitive effects.

Collectively, these results suggest that alcohol may compound the negative effects of HIV to generate greater levels of dysbiosis, microbial translocation, up-regulation of inflammatory pathways and seeding of the HIV reservoir. They also suggest that initiation of ART soon after HIV infection might: 1) dampen perturbations of GI microbiota, 2) reduce HIV-induced inflammatory changes, and 3) decrease seeding of the reservoir, although to a lesser degree in those with AUD. We will explore these questions in MSM/TGW (N~240) with acute or recent HIV infection, a large proportion of whom report high-level alcohol use. The proposed research will be conducted in MERLIN, as an extension of our ongoing study of acute and recent HIV infection among MSM/TGW in Peru, entitled the ‘SABES’ study. (<https://clinicaltrials.gov/ct2/show/NCT01815580?term=SABES&rank=1>).

4.3 PROBLEM UNDER INVESTIGATION

Results of several recent studies suggest that initiation of ART soon after HIV infection can reduce HIV-induced inflammatory changes and seeding of the reservoir. Clinical studies also suggest that early initiation of therapy can have a beneficial impact by reducing the HIV-associated morbidity that persists even when HIV replication is successfully achieved through ART. These studies leave open the question of how soon after HIV acquisition ART must be initiated to achieve these beneficial results. While initiation of ART during hyper-acute (Fiebig stages I and II) might seem optimal, detecting such individuals and linking them rapidly to care poses huge logistical challenges, not the least of which is instituting more wide spread screening for HIV infection using NAAT (nucleic acid amplification test). The intent of this study is to determine the impact of early treatment initiation among patients with acute (HIV RNA+/ seronegative) or very recent (HIV seropositive with a documented HIV RNA tested within the past 3 months) HIV infection. Most participants in this study participated in the SABES study (see below) and initiated ART early after HIV acquisition. Because participants were randomized to start ART at different times, the proposed studies will allow assessment of the relative impact of ART initiated at various times during the first year of infection. In addition, a small number of participants with chronic HIV infection and a small number of HIV-uninfected participants will be enrolled for comparison.

5. HYPOTHESIS

ART initiation during FI-II stages will largely prevent changes in GI microbiota and inflammatory markers, and reduce the size of the reservoir of replication-competent HIV.

- 1) Over time CD4 counts and peripheral inflammatory markers in seropositive participants who initiate ART 2 to 8 months after infection (ie in the Early and Deferred Arms) will approach those who initiated ART during Acute (FI-II) HIV; in contrast, we expect that these individuals initiating ART subsequent to acute infection will demonstrate persistent changes in the GI microbiome and in the HIV reservoir.
- 2) High-level alcohol use will compound the negative effects of HIV to generate greater levels of dysbiosis, microbial translocation, and up-regulation of inflammatory pathways, leading to increased seeding of the HIV reservoir prior to ART initiation. Early treatment should diminish, but not completely prevent, the changes in the microbiome associated with alcohol consumption and their impact on immune activation and seeding of the HIV reservoir.

6. OBJECTIVES

The overall objective is to determine the impact of time of ART initiation and high-level alcohol use on a number of HIV-related clinical parameters. These include time to viral suppression, CD4 count, HIV reservoir, changes in the gut microbiome and neurocognitive functioning.

6.1 PRIMARY OBJECTIVES

- 1) To determine the relative long-term benefits of immediate vs. early vs. deferred initiation of ART.

Initiation of ART during Fiebig I-II, while theoretically appealing, is currently infeasible in clinical practice because the duration of FI-II is very short (10 days) and because antibody-based tests, used almost world-wide, are unable to diagnose FI-II. Six months of ART initiated shortly after seroconversion (FIII) can improve many immune parameters, although not to the near normal level seen when ART is initiated during FI-II [3]. Longer-term follow-up of seropositive participants who started ART ~2-8 months after HIV acquisition compared to those initiating ART during FI-II is needed to see whether markers of inflammation and residual viral load might continue to improve after 6 months, decreasing the difference between the groups. Methods: We will evaluate the 3 groups using specimens from equivalent times after ART initiation through the first 5 years of ART usage, comparing CD4 counts, time to undetectable VL, GI microbiota, and inflammatory markers. The size of the replication-competent HIV reservoir in PBMCs will be compared using measurements of multiply spliced viral RNA (msRNA) and the degree of low-level infection of new cells by assessing the production of circular viral DNA (2LTR HIV DNA). We will model the size and persistence of the viral reservoir across all ART-adherent study participants. In a subset of individuals from each group, the proviral integration sites will

be defined at ART initiation and after 1.5 and 3.5 years to assess the maintenance of the reservoir by proliferating CD4 cells. We will continue evaluating endpoints annually or biannually, as long as participants remain on study.

- 2) To determine the impact of high-level alcohol use on the relative long-term benefits of immediate vs. early vs. delayed ART initiation

Dysbiosis is present in individuals with high-level alcohol use [23, 24, 27, 45-47] and in many HIV-infected patients. The extent of dysbiosis correlates with established markers of HIV disease progression and the consequent inflammatory processes contribute to HIV disease progression, even in treated individuals. *Methods*: We will use monthly self-report data on alcohol use as well as alcohol biomarkers in blood and hair to assess alcohol consumption as a continuous, time-varying predictor. In all participants at the time of diagnosis, and at multiple time points prior to ART in those enrolled into the deferred group, we will assess VL, GI microbiota, pro-inflammatory cytokines, and HIV reservoirs. We will compare these factors between subjects by their reported alcohol use, focusing on events occurring shortly after HIV acquisition. Specimens from uninfected and chronically infected subjects are available as controls. Finally, among ART-adherent subjects with persistent viral suppression, we will HIV DNA integration sites in those with and without high-level alcohol use at 1.5 and 3.5 years after ART initiation.

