14.3 ENDPOINTS

14.3.1 Primary Endpoints

- 1) To determine the relative long-term benefits of immediate vs. early vs. delayed initiation of ART.
 1. Measure the impact of early treatment on cell-activation, and inflammation by comparing cellular markers of inflammation in study participants who initiated treatment at varying times after HIV acquisition.
 2. Measure the impact of early treatment on the replication-competent HIV reservoir (size of the reservoir and types of cells involved) in study participants who initiated treatment at varying times after HIV acquisition.
 3. Determine whether early ART initiation prevents long-term changes in gastrointestinal tract bacterial microbiota and correlate these changes with systemic markers of inflammation and disease progression such as the activity of the kynurene pathway of tryptophan catabolism and plasma concentrations of the inflammatory cytokines.
 4. Document the impact of early ART initiation on 'non-HIV-associated' diseases

such as neurocognitive disorders. Assess the correlation of these clinical outcomes with laboratory markers of cell activation, inflammation and HIV reservoir size and characteristics.

5. Determine the impact of high-level alcohol use on the outcomes listed in 1-4, after controlling for time of ART initiation.

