14.6.2 MEASUREMENT OF THE HIV RESERVOIR

It is likely that early ART prevents the establishment of the long-lived latent reservoir, and this hypothesis is supported by several lines of evidence. However, to date almost all studies investigating this question have used PCR-based assays, which overestimate the size of the reservoir [12] because they do not distinguish between cells with defective, replication-incompetent cells vs. productively infected cells and the small pool of long-lived, latently infected cells. Conversely, the viral outgrowth assays measure only resting CD4+ T cells with replication competent HIV and likely underestimate the size of the reservoir [55]. Therefore, it is still unclear when and where the latent replication-competent reservoir is seeded. Our collaborator, [name], has recently developed a novel assay (Tat/Rev Induced Limiting Dilution Assay, "TILDA") that can more precisely measure the frequency of productively and latently infected cells in a clinical sample as various times after infection. This assay measures the frequency of cells harboring inducible HIV without the above-mentioned limitations of standard assays (Figure 2). By combining ultrasensitive detection of multiply spliced (ms) RNAs upon T cell receptor stimulation together with a limiting dilution assay, this method allows [name] lab to measure a frequency of cells harboring transcriptionally silent - nonetheless inducible – viruses. To our knowledge, this viral induction assay is the only method that allows the measurement of the frequency of cells harboring inducible virus that can be performed with less than a million CD4+ T cells.

[figure not shown]

Figure 2: HIV RNA induction assay. Sorted CD4+ T cells are stimulated for 12 hours with PMA/ionomycin. Serial dilutions of the stimulated cells are distributed in a 96-well plate and digested. Multi-spliced HIV RNA are detected in a 2-step real time PCR. The maximum likelihood method is used to calculate the frequency of cells with inducible HIV RNA based on the number of positive well.

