14.6.5 DNA INTEGRATION SITES

Drs. [name] and [name] will characterize and compare the HIV DNA integration sites in subjects with and without high-level alcohol use who started ART in Fiebig stages I-II, III-V and in the deferred ART arm. Among participants with sustained suppression of HIV RNA to undetectable levels, a total of 45 participants (~15 subjects from each group) will be studied upon enrollment (prior to the initiation of ART), and after 3.5 years of ART. PBMC from the subset of participants agreeing to leukapheresis will be preferentially selected for these studies.

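### Primary endpoint 2 names the replication-competent HIV reservoir, but the only assay named for its size counts cells with inducible HIV RNA, and the step between the two is assumed rather than stated

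*Protocol*

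**What the plan says.** The construct is named consistently. In section 14.3.1, item 2 of the primary endpoints reads: "Measure the impact of early treatment on the replication-competent HIV reservoir (size of the reservoir and types of cells involved"). The Executive Summary repeats that item in its first list of primary endpoints. Its second list uses the same term for the seeding of the reservoir close to HIV acquisition, which appears again as item 1 of section 14.3.2. The hypothesis in section 5 also predicts a smaller reservoir of replication-competent virus with ART started in Fiebig I-II.

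The measurement is fixed in section 6.1, under the methods for objective 1: "The size of the replication-competent HIV reservoir in PBMCs will be compared using measurements of multiply spliced viral RNA (msRNA"). The same sentence gives 2-LTR circles a different job: "the degree of low-level infection of new cells by assessing the production of circular viral DNA (2LTR HIV DNA").

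Section 14.6.2 explains the choice of assay. PCR-based assays are said to overestimate the reservoir because "they do not distinguish between cells with defective, replication-incompetent cells vs. productively infected cells". For the alternative, "the viral outgrowth assays measure only resting CD4+ T cells with replication competent HIV and likely underestimate the size of the reservoir". The protocol then adopts TILDA, stating: "This assay measures the frequency of cells harboring inducible HIV without the above-mentioned limitations of standard assays". The figure legend gives the readout after stimulation with PMA/ionomycin and limiting dilution: "Multi-spliced HIV RNA are detected in a 2-step real time PCR".

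**The concern.** The endpoint claims a property of the virus, the ability to replicate. The assay is described as detecting an earlier event, the appearance of multiply spliced RNA after stimulation. A provirus that can be transcribed to that point but is defective elsewhere would score positive. Section 14.6.2 raises exactly this objection against other PCR-based assays, then says that TILDA escapes it without giving a reason.

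What is at stake is the conclusion of a primary endpoint. A difference in inducible cells between the Immediate, Early and Deferred groups could be reported as a difference in replication-competent reservoir, or the absence of one as equality, when the data establish neither. Because duration of infection before ART is the exposure under study, an equal competent share across groups should not be taken for granted without being stated.

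**Working it through.** The protocol gives no figure for this point, so there is none to reproduce. The check is a comparison of texts followed by one identity.

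**Step 1. Construct against assay.**

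| Item | Where | What it refers to |
|---|---|---|
| Primary endpoint 2 | Executive Summary; 14.3.1 item 2 | Replication-competent reservoir: size and cell types |
| Hypothesis | 5 | Size of the replication-competent reservoir |
| Secondary endpoint 1 | 14.3.2 item 1 (Executive Summary, second list) | Seeding of the replication-competent reservoir |
| Measure of size | 6.1, objective 1 methods | Multiply spliced RNA |
| Named assay | 14.6.2 | TILDA: frequency of cells with inducible HIV, PCR readout |
| Assay tied to replication competence | 14.6.2 | Viral outgrowth; discussed as background, not listed for this study |

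**Step 2. Does any described step of TILDA show competence?** The steps given are sorting CD4+ T cells, stimulation, serial dilution in wells, digestion, PCR for multiply spliced RNA, and a maximum likelihood estimate from the number of positive wells. None observes infectious virus. Requiring induced RNA excludes proviruses that cannot be transcribed, so the defective-provirus problem is reduced. Nothing described removes it.

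**Step 3. What the substitution requires.** For an ART-timing group let

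- T = frequency of cells positive for inducible multiply spliced RNA (measured),
- f = share of those cells whose virus is replication-competent (not given in the documents),
- R = f × T = frequency of replication-competent cells among those detected.

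For groups 1 and 2:

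R1/R2 = (T1/T2) × (f1/f2).

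If f1 = f2, then R1/R2 = T1/T2: the relative comparison is undistorted, although T exceeds R by a factor 1/f in each group.

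**Step 4. Range under an assumption.** Assume f1/f2 lies between 0.5 and 2. With an observed T1/T2 = 1.0:

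- lower end: R1/R2 = 1.0 × 0.5 = 0.5;
- upper end: R1/R2 = 1.0 × 2 = 2.0.

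**Step 5. Both directions.** Let group 1 be Immediate and group 2 Deferred.

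- Truly equal reservoirs (R1/R2 = 1) with f1/f2 = 2 (for instance 0.4 against 0.2, both assumed) give T1/T2 = 1/2 = 0.5, an apparent halving with immediate ART.
- A true halving (R1/R2 = 0.5) with f1/f2 = 0.5 gives T1/T2 = 0.5/0.5 = 1.0, so a real benefit is hidden.

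Data on multiply spliced RNA alone cannot separate these cases, because f does not enter the measurement.

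**The case against.** The strongest reply is that the protocol deals with the issue openly. Section 14.6.2 describes one class of assay that overestimates and another that likely underestimates, and places TILDA between them. It calls the target inducible virus throughout, so an attentive reader can see that a surrogate is in use. Primary objective 1 concerns relative benefit between groups, and a common f cancels from a ratio. All of this stands. TILDA is a reasonable choice and nothing here asks for its replacement. What the reply does not supply is a statement that inducible RNA stands in for replication competence, or the condition under which it does.

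Several stronger readings are tempting, and the documents do not support them:

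- A reader might infer that the trial can say nothing about the replication-competent reservoir. It can, under the equal-share condition; the defect is that the condition is left unstated and untested.
- A reader might infer that 2-LTR DNA and the integration-site work are failed measures of this endpoint. Section 6.1 gives 2-LTR DNA to new-cell infection and does not say how it is detected. Section 14.6.5 sets out to "characterize and compare the HIV DNA integration sites in subjects with and without high-level alcohol use", and section 6.1 uses that work to study maintenance of the reservoir by proliferating cells. Neither is offered as the size of the replication-competent reservoir.
- A reader might infer that no measurement of competence is planned at all. Section 10.3.4.10, including as revised by Amendment Letter 2, schedules leukapheresis for qualitative and quantitative reservoir work, and section 15.1 plans reservoir assays without naming them. An assay list may exist elsewhere. The supportable statement is that no assay named in this protocol establishes competence.
- A reader might infer a bias in favour of immediate ART. No passage says how often RNA-positive cells carry defective virus, or that this varies with time to ART.

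An analysis plan could not settle the matter, since the protocol itself fixes both the construct and its assay.

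**Conclusion.** The wording is wrong as it stands, within narrow limits. A primary endpoint, the hypothesis, the methods of objective 1 and a secondary endpoint name a property that no named assay establishes, and the claim in 14.6.2 that TILDA is free of the earlier limitations is not supported for transcribed but defective provirus. Comparison of the inducible reservoir across ART-timing groups is unaffected.

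The size of any error in the replication-competent comparison cannot be derived from the documents. Under the assumed range of 0.5 to 2 for f1/f2, an observed ratio of 1.0 is compatible with 0.5 to 2.0; with f1 = f2 there is no relative error. The range is illustrative and two-sided. No sample size, power or alpha figure is involved.

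**What to change.** 1. In both endpoint lists of the Executive Summary, section 5, section 6.1 (objective 1 methods), section 14.3.1 item 2 and section 14.3.2 item 1, restate the measured quantity as the inducible HIV reservoir: the frequency of CD4+ T cells with inducible multiply spliced HIV RNA by TILDA, together with the cell types involved. Say that it is a surrogate for the replication-competent reservoir. Keep the cell-type component, which is part of the endpoint.
2. In section 14.6.2, remove the clause saying that the assay is free of the limitations of standard assays, and state that TILDA does not establish replication competence.
3. Limit conclusions on this endpoint to the inducible reservoir.

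The cost is wording only: no samples, visits or assays change. The downside is a narrower claim than the protocol now makes.
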